To test the hypothesis that reduction in myocardial triglyceride content will improve markers of diastolic function, we have designed a randomized, double blind, placebo controlled trial. To recap, we will study four groups of previously sedentary obese middle aged subjects at high risk for development of HF for one year with the following interventions: A) sedentary controls taking placebo; B) sedentary subjects taking omega-3 fatty acids; C) subjects undergoing high intensity aerobic exercise training while on placebo and D) subjects undergoing high intensity aerobic exercise training while taking omega-3 fatty acids. We anticipate the combination of high intensity aerobic exercise in conjunction with high dose omega-3 supplementation will reduce visceral adiposity, decrease myocardial triglyceride content and improve markers of diastolic and vascular function.

We will need to complete baseline testing on 80 subjects to enter the 1 year intervention with 44 assigned to exercise and 36 to yoga control. This difference is designed to account for differences in compliance within the 2 exercise groups. Within each exercise/yoga group, half of subjects will be randomized to placebo or omega-3 fatty acid supplementation. For the exercisers, 22 subjects will be given placebo and 22 will be given omega-3. For the yoga control, 18 will receive placebo and 18 will receive omega-3. Ultimately the study is powered to end up with 15 subjects per group (total N=60) accounting for drop outs to complete all follow up testing (please see “power calculations” section on page 697 (of 731) of the AHA grant, submitted as “protocol” which develops and supports these numbers in some detail).

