- 2) Arterial compliance testing: Used to determine the flexibility of the arteries. We will obtain blood pressure measurements through several different non-invasive techniques and take pictures of the arteries using ultrasound. The arteries that we will examine include the arteries in the wrist, elbow, neck, groin, and stomach. We will also collect approximately 4 tablespoons of blood to measure serum biomarkers of cardiac and metabolic health.
- 3) Body composition analysis: Used to determine the body's muscle, fat, and water composition using skin caliper technique and underwater weighing techniques. First, we will obtain detailed measurements of height, weight, skinfold thickness, etc., using measuring tape and calipers. There is no risk with this procedure, though some individuals experience some pinching from the calipers. We will also measure body composition using DEXA scanning. There is very low dose radiation associated with the

scan, about 1/10th the dose of an x-ray. Prior to a DEXA, we will perform a routine pregnancy test to ensure that subjects are not pregnant before undergoing the scan.

“Baseline” Day 3: Magnetic Resonance Imaging - The 3rd day is devoted to MRI, and includes measurements of LV mass, aortic compliance, MR spectroscopy for the assessment of myocardial triglyceride concentration, and delayed enhancement imaging for quantification of fibrosis. We have developed an integrated protocol which starts with the anatomic images for measurements of cardiac and vascular morphology followed by spectroscopy for triglyceride content. This visit will usually last between 3-4 hours; no blood draws are performed during this visit.

Experimental Intervention:

The experimental intervention involves randomization into one of four groups. This randomization is designed to assess the impact of omega-3 fatty acids and high intensity aerobic exercise training versus placebo. A more detailed description of the “Experimental Intervention” is included in the STUDY DESIGN section of this document.

“Mid Progress Testing” Procedure: At 6 months into the experimental intervention, subjects will return to the lab for mid-progress testing. This day is identical to “baseline day 2” and allows us to gauge adequacy of the exercise training intervention as well as to assess changes in body composition.

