“Follow-up Testing” Procedure: At the conclusion of the one year experimental intervention, follow-up testing will be performed to assess the effects of the intervention. The “Follow-up Testing” protocol is similar to “Baseline Testing” with the omission of the “Baseline” Screening Procedure and “Baseline” Study Day 1.

“Follow-up” Day 1: This day is identical to “Baseline” Day 2 with the additional measurement of 24 hour ambulatory blood pressure.

“Follow-up” Day 2: This day is identical to “Baseline” Day 3.

At the conclusion of the “Follow-up Testing”, each subject will have completed our study and reimbursement will be distributed.

Regarding the storage of blood samples, we will retain whatever blood is left over after all the analyses are complete in case other blood tests become available that might be useful to explain the effects of aging and obesity on the heart. The samples will be kept in the freezer in the biochemistry lab at the IEEM with a code to specify from which patient it comes and the study date. Only the Principal investigator and biochemistry lab staff will have access to these samples.

Criteria for Inclusion of Subjects:

One hundred twenty healthy, sedentary men and women ages 40-60 will be recruited to start the intervention on 80 who complete all baseline testing. The key inclusion and exclusion criteria are as detailed in the SUBJECT POPULATION section above. To recap, subjects will be recruited based on 1) the presence of high visceral adiposity (>2.5 kg) assessed by either MRI or DEXA scan, 2) a normal ejection fraction ($>50\%$); 3) elevated serum biomarkers of sub-clinical cardiac injury (cardiac troponin T, brain-type natriuretic peptide) and 4) obesity with BMI range $30 - 50$ kg/m^2 . Subjects will be recruited from the DHS and CCLS without regard to race or gender.

Criteria for Exclusion of Subjects:

Exclusion criteria include age < 40 or > 60 , body mass index > 50 , $< 30 \text{ kg}/\text{m}^2$ and any history of insulin dependent diabetes, heart failure, myocarditis, restrictive cardiomyopathy, permanent/persistent atrial fibrillation, severe chronic obstructive pulmonary disease, unstable coronary artery disease or recent (<12 month) acute coronary syndrome, cerebrovascular disease as evidenced by prior transient ischemic attack or stroke and active/recent tobacco use (quit < 5

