**NCT number: NCT03448185**

**Document date: 1/6/2014**

## Power Calculations

Per protocol analysis will be performed and include only subjects who have completed at least 80% of the prescribed training. The primary outcome for this aim will be reduction in cardiac lipid content after intervention targeting visceral fat. Myocardial triglyceride content in obese subjects with metabolic syndrome is approximately 0.9% with a standard deviation of 0.4%. We anticipate a reduction of approximately 50% to 0.45% based on prior studies. In a 2x2 design with subjects randomized to HIIT or yoga and O3-PUFA or placebo, 60 subjects will need to be enrolled to detect an absolute reduction in mean TG content to 0.45% (from 0.9%) with a standard deviation of 0.4%, alpha of 0.05 and power of 80%. To analyze the cardiac effects of reducing visceral adiposity between groups, a mixed model repeated measures analysis will be used for continuous variables such as LV mass index, LV concentricity index, and diastolic strain adjusting for age, sex and hypertension. Descriptive statistics will be used to characterize changes in anthropomorphic parameters (e.g. BMI, lean body mass) and serum biomarkers (cTnT, NT-proBNP) using a 3 factor (time, exercise, drug) repeated measures analysis of variance between the four groups.

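### The SAP does not say how an outcome's baseline value enters the analysis; prespecifying ANCOVA on baseline would gain precision for one degree of freedom, mainly in the 15 v 15 comparisons

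*SAP*

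**What the plan says.** The SAP (Power Calculations) defines the primary outcome: "The primary outcome for this aim will be reduction in cardiac lipid content after intervention targeting visceral fat". Its planning values are cross-sectional: "Myocardial triglyceride content in obese subjects with metabolic syndrome is approximately 0.9% with a standard deviation of 0.4" percent, with an anticipated fall to 0.45%. It then assigns a repeated-measures mixed-model "analysis will be used for continuous variables such as LV mass index, LV concentricity index, and diastolic strain adjusting for age, sex and hypertension". Triglyceride is not named in that open list and may or may not belong to it. No other model is given for it. Time is named as a factor only in the separate ANOVA for anthropometric measures and serum biomarkers.

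The analysis set is restricted: "Per protocol analysis will be performed and include only subjects who have completed at least 80% of the prescribed training".

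The Protocol (Study Procedures) fixes the measurement times. Baseline Day 3 is the MRI day and includes "MR spectroscopy for the assessment of myocardial triglyceride concentration". The six-month visit repeats Baseline Day 2, which has no MRI; it "allows us to gauge adequacy of the exercise training intervention as well as to assess changes in body composition". At the end of the year "follow-up testing will be performed to assess the effects of the intervention", and Follow-up Day 2 repeats the MRI day.

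On size, the Protocol (Study design) says: "Ultimately the study is powered to end up with 15 subjects per group (total N=60) accounting for drop outs". Its Biostatistics section claims 99% power for a main effect and 80% for comparisons of individual groups. It refers to a fuller statistical section in the grant, which is not among the documents supplied.

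**The concern.** The listed adjustments are age, sex and hypertension. The variable likely to be most prognostic for 12-month triglyceride is its own baseline value, and the text does not say how that value is handled. With two visits, a repeated-measures model can be set up in two ways that differ in precision. With separate baseline means for each group, the treatment test is a comparison of change scores. With one common baseline mean, the same model has the variance of ANCOVA. The SAP wording allows either.

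Precision matters most in the comparisons of individual groups, which have 15 completers each and only 80% claimed power. Baseline MRI is already collected in everyone who starts the intervention, so the gain needs no further data.

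There is also a prespecification issue. When groups differ at baseline by d, the change-score and ANCOVA estimates differ by (1−r)d. In a per-protocol set randomisation no longer guarantees balanced baselines, so an unstated form leaves a choice between two different estimates after the data are seen.

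**Working it through.** **Inputs.** Difference 0.45, SD 0.4 and alpha 0.05 (SAP, Power Calculations); 15 per group, so 30 v 30 for a main effect (Protocol, Study design). Assumptions of this review: two-sided tests, SD 0.4 at both visits, and 0.45 as both the main effect and the pairwise difference. The correlation r is not in the documents and is shown at 0.3, 0.5 and 0.7.

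**Step 1: the plan's own figures, using SD 0.4 with no baseline correlation.**
- Main effect, 30 v 30: SE = 0.4 × √(2/30) = 0.103; 0.45/0.103 = 4.36. Power is 0.992 (normal) or 0.990 (t, 56 df), which reproduces the stated 99%.
- Group comparison, 15 v 15: SE = 0.4 × √(2/15) = 0.146; 0.45/0.146 = 3.08. Power is 0.869 (normal) or 0.857 (t, 56 df). The stated 80% is reproduced if alpha is 0.025 (0.799, normal), a split that the documents do not mention.

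**Step 2: the two forms.**
- SD of change = 0.4 × √(2(1−r)).
- ANCOVA residual SD = 0.4 × √(1−r²).
- Variance ratio = 2(1−r)/(1−r²) = 2/(1+r).

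The change model has intercept, exercise, drug, interaction, age, sex and hypertension: 60 − 7 = 53 df. ANCOVA adds baseline: 52 df. Power is by noncentral t at unadjusted two-sided 0.05. Paired entries are change v ANCOVA.

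| r | SD | Variance ratio | Power, 15 v 15 | Difference detectable at 80% power, 15 v 15 | Power, main effect 30 v 30 |
|---|---|---|---|---|---|
| 0.3 | 0.473 v 0.382 | 1.54 | 72% v 89% | 0.49 v 0.40 | 95% v 99% |
| 0.5 | 0.400 v 0.346 | 1.33 | 86% v 94% | 0.42 v 0.36 | 99% v >99% |
| 0.7 | 0.310 v 0.286 | 1.18 | 97% v 99% | 0.32 v 0.30 | >99% v >99% |

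From r = 0 to r = 0.9 the excess variance of change scores runs from 100% to 5%. A simulation of 20,000 trials (four groups of 15, three non-prognostic covariates in both models) gave 15 v 15 power of 70% v 86%, 84% v 92% and 97% v 98%.

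**Step 3: where change-score power drops below 80% at 15 v 15.** This happens when r is below about 0.42 at alpha 0.05, below 0.52 at alpha 0.025, and below 0.63 with Bonferroni correction for all six pairwise comparisons. The threshold depends on an alpha that the plan does not state for these comparisons. At r = 0.5 with six Bonferroni-corrected comparisons, and without the three extra covariates, power is 0.636 v 0.790.

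**Step 4: effect on the estimate.** A baseline difference of one standard error at 15 v 15 is d = 0.146. The two estimates then differ by (1−r)d = 0.102, 0.073 and 0.044. Divided by 0.45, that is 23%, 16% and 10% of the planned effect.

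**The case against.** **Baseline is probably already used.** With MRI at two visits, a repeated-measures model of an MRI outcome has to carry baseline as a response. A reader might infer from the covariate list that the plan ignores baseline. The documents do not support that, and adding baseline as a covariate to the same model would use it twice. If baseline means are held equal, no precision is lost. This objection stands: the gap is in the specification and does not demonstrate a loss.

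**The power claim is not refuted.** A reader might infer that the stated 80% is wrong. It is not shown to be. It holds under change scores for r above the thresholds in the working, and under ANCOVA at all three illustrated values at unadjusted alpha 0.05. At r = 0.7 the pairwise gain is only from 97% to 99%, and main effects have little to gain.

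**The quoted model names other outcomes.** The figures here are for triglyceride because only triglyceride has planning values. The ratio 2/(1+r) applies equally to LV mass index, concentricity and strain, given equal variances and two visits, but their r is also unknown.

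**The precision argument is clean only for randomised groups.** This also stands. In the per-protocol set a systematic baseline difference can bias either estimator. If it would have persisted without treatment, ANCOVA is off by (1−r)d. If it would have shrunk to rd, change scores are off by the same amount. The SAP also anticipates a proportional fall of about 50%, which may strain a single common baseline slope.

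**The grant may settle the matter.** If its fuller statistical section already fixes the form, the SAP need only restate it.

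**Conclusion.** The point holds as a low-cost improvement in precision and prespecification. The supplied text does not say how baseline enters and names no model for the primary outcome. If baseline means are left free, variance is 1.54, 1.33 or 1.18 times that of ANCOVA at assumed r of 0.3, 0.5 or 0.7. In power terms, ANCOVA adds about 16, 8 or 1 to 2 percentage points to a 15 v 15 comparison of triglyceride (0.887 − 0.725, 0.937 − 0.857, 0.989 − 0.974).

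These sizes rest on SD 0.4 at both visits, a 0.45 pairwise difference, unadjusted two-sided alpha 0.05 and the assumed r. The conclusion covers only the text supplied. It does not show an error in the stated power. Nor does it show that ANCOVA removes bias in the per-protocol set, where the selection problem remains whichever form is used.

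**What to change.** Replace the two-visit repeated-measures model; do not add a covariate to it. Specify ANCOVA of the 12-month value on the outcome's own baseline, exercise, drug, exercise × drug, age, sex and hypertension. Name it as the primary analysis for triglyceride, and use the same form for LV mass index, concentricity and diastolic strain.

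Beside the sample size, state the assumed baseline-to-12-month correlation and the alpha used for pairwise comparisons.

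In any analysis of all randomised participants, a mixed model with baseline means constrained equal is an equivalent alternative. That constraint should not be imposed in the per-protocol set. For that set, state that baseline adjustment improves precision but does not remove selection, and that systematic baseline differences can bias either ANCOVA or change scores.

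The cost is SAP wording and one degree of freedom (53 to 52 with 60 completers). All planned covariates stay, and no extra participants, visits or measurements are needed.

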However, not every subject who enrolls in the study will go onto complete testing. During testing, exclusion criteria may be identified requiring disqualification from the study; examples include the identification of coronary artery disease by cardiopulmonary stress testing. Furthermore, subjects may wish to withdraw from testing for personal or health related reasons. This requires “enrolling”, or consenting, a total of 120 subjects. We plan to enroll these 120 subjects over an 18-month period and will halt enrollment after 80 volunteers have completed all pre-testing as described above. Ideally, our protocol can be completed in 12-14 months; however, unexpected interruptions occasionally occur, extending the protocol up to as much as 24 months. With these delays taken into consideration, we expect to conclude our study in roughly 36 months (3 years). All enrollment and testing will be performed at our facility, making this a

single site study.

Following completion of the baseline studies, volunteers will be randomized to either an exercise intervention, or yoga/Tai Chi control. Subjects will be stratified by sex and allocated to the either exercise or yoga intervention using a stratified block randomization at a 1.2 to 1 exercise to yoga ratio (allowing for greater attrition for the exercise group). The randomization schema will be programmed using SAS Proc Plan and performed by [name], a biostatistician on our team. An active yoga/Tai Chi control allows for equipoise for the volunteers by improving quality of life without affecting fitness. It also controls for the contact with study staff; we are using this approach for the non-exercise controls in our current clinical trial (NCT02039154).

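### Exercise-versus-yoga allocation is stratified by sex, but the SAP's three-factor ANOVA omits sex, and its mixed model does not say that sex acts on the change from baseline

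*SAP*

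**What the plan says.** **Allocation.** Protocol, Study design: "Subjects will be stratified by sex and allocated to the either exercise or yoga intervention using a stratified block randomization". The planned split favours exercise by 1.2 to 1. For the capsules the same section says: "Within each exercise/yoga group, half of subjects will be randomized to placebo or omega-3 fatty acid supplementation". It names no sex stratum for that second step.

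**First analysis.** SAP, Power Calculations: a repeated-measures mixed model is planned for cardiac outcomes, namely "LV mass index, LV concentricity index, and diastolic strain adjusting for age, sex and hypertension". The SAP does not say whether baseline is a response or a covariate, whether the covariates interact with visit, or which term is the treatment effect.

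**Second analysis.** Same section, for body measures and serum biomarkers: "using a 3 factor (time, exercise, drug) repeated measures analysis of variance between the four groups". Sex is not among the factors.

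**Visits.** Protocol, Study Procedures: MRI is done on Baseline Day 3 and repeated on Follow-up Day 2. The 6-month visit repeats Baseline Day 2, which has no MRI; its stated purpose is that it "allows us to gauge adequacy of the exercise training intervention as well as to assess changes in body composition".

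**The concern.** A factor used to stratify the randomisation normally belongs in the analysis. Stratifying balances that factor between arms and so removes its contribution from the true sampling error of the treatment difference. A model that ignores the factor leaves this contribution in the residual variance, so its standard error overstates the real uncertainty.

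The ANOVA leaves sex out altogether. The mixed model lists sex, but listing it may not be enough. When the treatment effect is a difference in change, a fixed characteristic that adds the same amount at each visit may drop out of that difference. Readers would then take the cardiac results as adjusted for age, sex and hypertension although the treatment contrast was untouched. Some precision is also at stake. The error is on the conservative side and creates no extra false positives.

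**Working it through.** **Inputs**
- Sex strata for exercise v yoga, planned 44 v 36 (Protocol, Study design). 44/36 = 1.22, which agrees with the stated ratio.
- Planned completers: 15 per group, so 30 v 30 for exercise v yoga (Protocol, Study design).
- Two MRI visits, baseline and 12 months (Protocol, Study Procedures).
- R2, the share of the variance of 12-month change explained by sex: not in the documents. Assumed 0, 5, 10 and 20%.

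No figure in the plan depends on this point, so there is none to reproduce. The sample size of 60 does not enter.

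**Step 1: when a covariate cancels.** Let T be treatment, S sex and u the subject effect, with baseline as a response and free baseline means:
- Baseline: Y0 = a + bT + cS + u + e0
- 12 months: Y1 = a + d + (b + g)T + cS + u + e1
- Change: Y1 − Y0 = d + gT + (e1 − e0)

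The term cS is gone, so with complete pairs neither the estimate of g nor its standard error depends on it. With a sex-by-visit term hS the change becomes d + gT + hS + (e1 − e0), and sex then acts on the contrast. The same algebra applies to the ANOVA: a sex main effect alone would not reach the time-by-exercise contrast, so the useful term is sex-by-time.

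**Step 2: numerical check.** One simulated data set: 60 subjects, equal numbers of each sex, within-visit variance 1, correlation 0.6, and an assumed sex effect on change of 0.8 SD. Exercise estimate (SE):

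| Model form | Without covariates | With age, sex, hypertension |
|---|---|---|
| Baseline a response, free means, covariates as main effects | −0.8991 (0.3341) | −0.8991 (0.3341) |
| Same, covariates by visit | −0.8991 (0.3341) | −0.8501 (0.3037) |
| Baseline a response, common baseline mean, covariates as main effects | −0.8977 (0.3062) | −0.9145 (0.2874) |
| Baseline as a covariate (ANCOVA) | −0.8989 (0.3368) | −0.8753 (0.2769) |

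Cancellation is exact in the first row only.

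**Step 3: incomplete pairs.** In further simulations (N = 60, 25 data sets per setting) 3 or 6 follow-up values were missing. Main-effect covariates then moved the estimates slightly but left the mean SE unchanged (0.276 v 0.276; 0.285 v 0.285). Covariate-by-visit terms lowered it to 0.265 and 0.272.

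**Step 4: size if sex predicts change.** With sex balanced between arms, the SE ratio (sex ignored v used) is 1/√(1 − R2). By the normal approximation, the true type I error of a nominal two-sided 5% test is 2[1 − Φ(1.96/√(1 − R2))]. The last column gives the range over two simulations in which 44:36 falls at random to 30:30, so that sex balance is no longer exact.

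| R2 (assumed) | SE ratio | Type I error, exact balance | Type I error, after random loss |
|---|---|---|---|
| 0 | 1.000 | 5.0% | not run |
| 5% | 1.026 | 4.4% | 4.4–4.7% |
| 10% | 1.054 | 3.9% | 4.2% |
| 20% | 1.118 | 2.8% | 3.3–3.6% |

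Example, R2 = 10%: 1/√0.90 = 1.054; 1.96 × 1.054 = 2.066; two-sided tail 3.9%.

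**Step 5: size if sex shifts level only.** With sex moving the outcome by 1 or 2 SD at both visits and not affecting change, the mean SE of the change contrast was the same with and without sex (0.2295 and 0.2295; 0.2307 and 0.2307). Nothing is lost.

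**The case against.** The strongest objection is that the SAP does state adjustment for sex, and that the cancelling model is only one way to read a sentence that leaves the model open. This stands. A reader might infer that neither analysis lets sex affect the treatment comparison and that the stated adjustment does nothing. The documents do not support that: cancellation needs free baseline means, main-effect covariates and complete pairs, and the SAP states none of these. A common-baseline model or covariate-by-visit terms escape it. So do ANCOVA and a change-score model, although with a single post-baseline MRI these leave one row per subject and fit the SAP's repeated-measures label less well.

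Other limits also stand:
- The per-protocol set is defined by training adherence, not by having both scans, so pairs may be incomplete. Step 3 suggests this makes little difference to the standard error.
- Hypertension cancels only if one fixed status is used, and the SAP does not say which. The Protocol's MRI day does not name diastolic strain, so the two-visit premise is not shown for that variable.
- The ANOVA is introduced as descriptive, for outcomes that are neither primary nor secondary in the Protocol's Biostatistics section. Still, a repeated-measures ANOVA between four groups yields tests and standard errors.
- Neither model is expressly tied to the primary outcome, myocardial triglyceride, so no loss can be claimed for it.
- A reader might infer that the capsule allocation ignores sex. The Protocol is silent on this, so the stratification argument covers exercise v yoga only.

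**Conclusion.** The point holds in a limited form. It is certain that exercise v yoga is stratified by sex and that the three-factor ANOVA has no sex term. It is plausible, but not established, that sex, age and hypertension would cancel from the treatment contrast in the mixed model for two-visit MRI outcomes.

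A reader might go on to infer that the standard errors are too wide. That follows only if sex predicts 12-month change, and the documents give no figure. For an assumed R2 of 5% to 20% the exercise-versus-yoga standard error is about 2.6% to 12% too wide, with type I error of about 4.4% falling to about 3%. Adherence losses weaken the sex balance and bring the type I error somewhat nearer to 5%. At R2 = 0 there is no loss. No power figure is offered, because the documents state no effect size for these outcomes. This is a nearly costless improvement and does not threaten the trial's conclusions.

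**What to change.** In the SAP, Power Calculations:
1. Add sex and sex-by-time to the three-factor ANOVA.
2. In the mixed model, enter sex by visit and name the visit-by-treatment term as the treatment contrast, so that the stated adjustment acts on it.
3. Optionally, enter baseline age and baseline hypertension by visit as well.

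The cost of items 1 and 2 is a few words. In simulation at N = 60, sex-by-visit changed the standard error by no more than 0.2% when sex does not predict change (ratio 0.998 to 1.000). Item 3 is a trade-off. With all three covariates by visit, the ratio of the standard error to that without them was 1.029, 1.002, 0.973 and 0.921 when R2 was 0, 5, 10 and 20%. That is about 3% wider if none of the three predicts change, no gain at 5%, and a gain from 10% upwards. The randomisation need not change.

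### Body composition and biomarkers with three planned visits are assigned to repeated measures ANOVA, although the mixed model named in the same SAP paragraph would use incomplete follow-up better

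*SAP*

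**What the plan says.** The SAP is one paragraph, headed Power Calculations. It opens with the analysis set: "Per protocol analysis will be performed and include only subjects who have completed at least 80% of the prescribed training". For cardiac effects, "a mixed model repeated measures analysis will be used for continuous variables such as LV mass index, LV concentricity index, and diastolic strain", adjusted for age, sex and hypertension. The next sentence takes BMI, lean body mass, cTnT and NT-proBNP, calls the analysis descriptive, and carries it out "using a 3 factor (time, exercise, drug) repeated measures analysis of variance between the four groups".

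The visit schedule is in the protocol. Under Mid Progress Testing, "At 6 months into the experimental intervention, subjects will return to the lab for mid-progress testing". That day repeats Baseline Day 2 and is meant to gauge the training "as well as to assess changes in body composition". Baseline Day 2 includes DEXA, anthropometry and the blood draw for cardiac and metabolic biomarkers. Follow-up Day 1 repeats Baseline Day 2 after one year. These outcomes therefore have three planned measurements.

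Under Study design, 80 subjects start, "44 assigned to exercise and 36 to yoga control", and 15 per group (60 in all) are expected to complete follow-up. Neither document states how missing values are handled, how the ANOVA is fitted, or on what scale cTnT and NT-proBNP are analysed.

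**The concern.** Classical repeated measures ANOVA needs a value at every visit. A subject who gives a 6-month result and then leaves contributes nothing, and neither does a subject who attends at 12 months but missed month 6. A likelihood-based mixed model uses whatever follow-up values exist.

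The allocation of methods is also awkward. LV mass is an MRI measure, and MRI is scheduled only at baseline and 12 months, yet the cardiac outcomes get the mixed model. The ANOVA goes to outcomes that have an intermediate visit, where a mixed model has more to offer.

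Two things are at stake: precision, and the comparison of selected completers when loss is expected to differ between arms. The descriptive label does not remove either, because a three-factor ANOVA across four groups is still a between-group analysis.

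The scale of the biomarkers is a smaller matter. Entry under Subject Population requires a positive high-sensitivity troponin or a natriuretic peptide in the top quartile, so a skewed distribution is plausible. The documents give no distribution for either marker.

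**Working it through.** **Inputs.** From the protocol, Study design: 44 exercise and 36 yoga at the start; 15 completers in each of four groups, so 30 per exercise arm. From the protocol, Biostatistics: 99% power for a main effect. From the SAP: difference 0.45, SD 0.4, alpha 0.05 (two-sided assumed).

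**Step 1: the plan's own figure.** With 30 v 30, z = 0.45 / (0.4 × √(2/30)) = 4.36, and power = Φ(4.36 − 1.96) = 99.2%. This reproduces the stated 99%, so 60 is the number the plan expects to analyse. That power concerns the primary outcome and is not in dispute here.

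**Step 2: implied loss.** Overall 20/80 = 25%. Exercise (44 − 30)/44 = 14/44 = 31.8%. Yoga (36 − 30)/36 = 6/36 = 16.7%.

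**Step 3: within the per-protocol set.** Take the 60 completers as that set. The documents give no rate of missed 6-month visits, so 0–20% is assumed.

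| Completers missing month 6 (assumed) | Complete-case ANOVA | Mixed model |
|---|---|---|
| 0% | 60 | 60 |
| 5% | 57 | 60 |
| 10% | 54 | 60 |
| 20% | 48 | 60 |

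If no one misses a visit, changing the model alone gains nothing.

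**Step 4: 6-month exercise contrast, all randomised subjects.** Assume all 20 lost subjects have a 6-month value and all 60 completers have all three. The relative width of the complete-case interval is √[(1/30 + 1/30)/(1/44 + 1/36)] = √(0.06667/0.05051) = 1.149. If fewer of the 20 were seen at 6 months, the ratio falls toward 1.

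**Step 5: 12-month exercise contrast (change from baseline), all randomised subjects.** Assume within-person correlation 0.5–0.9, equal between any two visits; values missing completely at random; and half of the dropouts seen at 6 months. The variance is compared between complete cases and a mixed model using all available values.

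| Completers missing month 6 (assumed) | Variance ratio | Width ratio (square root) |
|---|---|---|
| 0% | 1.04–1.08 | 1.02–1.04 |
| 10% | 1.16–1.20 | 1.08–1.09 |
| 20% | 1.30–1.35 | 1.14–1.16 |

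**Step 6: baseline as a covariate.** Step 5 treats baseline as one of three outcomes, so subjects with a baseline value only still contribute. With baseline as a covariate they do not. For n completers and m subjects seen only at 6 months, the 12-month variance is multiplied by 1 − r² × m/(n + m), where r = ρ/(1 + ρ). Per cell, m/(n + m) is 3.5/18.5 = 0.189 in exercise and 1.5/16.5 = 0.091 in yoga, average 0.140.
- ρ = 0.5: r² = 0.111, factor 1 − 0.0156 = 0.984, width ratio 1/√0.984 = 1.008.
- ρ = 0.9: r² = 0.224, factor 1 − 0.0314 = 0.969, width ratio 1/√0.969 = 1.016.

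With no missed 6-month visits, the gain at 12 months is then nearer 1–2%.

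**The case against.** The strongest reply is that the per-protocol rule, not the ANOVA, is the main cause of lost subjects. It removes many of those who stop early before any model is fitted, and a mixed model in the same set would still compare selected completers. This stands. A reader might infer that the mixed model alone would keep the 20 expected losses; it would not. Moreover, the protocol ties the 44/36 split partly to compliance, so some of the 14 and 6 may be non-compliers who still attend visits.

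Second, the SAP nowhere says that subjects with a missed visit are dropped. A time-by-exercise-by-drug model can be fitted by likelihood, and the SAP itself does not mention a 6-month visit; if time meant only before and after, a missed month 6 would remove no one. This stands as a limit on certainty. But naming ANOVA beside a separately named mixed model most naturally means the classical method, and the protocol schedules three visits.

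Third, a reader might infer that the biomarkers will be analysed untransformed. The SAP is silent on scale, and since entry needs only one of the two markers raised, neither need be high in every subject.

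Fourth, these are not the only outcomes measured at 6 months. Exercise testing and arterial compliance are repeated that day too, and the protocol's risk section adds liver tests and lipids. Visceral fat is not named in the ANOVA sentence, so its importance cannot be borrowed for this point.

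**Conclusion.** The point holds as a minor one. For outcomes with three planned visits and unequal expected loss, the likelihood-based mixed model is the better method, and the SAP already names it for other outcomes.

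The size is modest and depends on the analysis set:

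- With the per-protocol rule kept, the gain is limited to compliant subjects who missed a visit, at a rate the documents do not give.
- With all randomised subjects included, complete-case intervals at 6 months are at most about 1.15 times as wide when the 60 completers have every visit. That maximum requires all 20 lost subjects to have 6-month data.
- At 12 months, with all randomised subjects and no completer missing month 6, the difference is about 2–4% in width, slightly less with baseline as a covariate, and more if completers miss that visit.

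It would be wrong to read the 15% as a general cost of the ANOVA, or to carry it over to the primary outcome. These outcomes are supportive, and neither the myocardial triglyceride analysis nor the sample size is affected. Bias from the 15-point difference in loss is possible, but the documents give nothing from which to estimate it.

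**What to change.** For body composition and the serum biomarkers, replace the ANOVA with the SAP's mixed model, fitted by likelihood:

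- **Model.** Outcomes are the 6- and 12-month values, with the baseline value as covariate and terms for exercise, drug, their interaction and time. Let the treatment effects differ by visit, and keep the existing adjustment for age, sex and hypertension.
- **Population.** All randomised subjects with any follow-up value. Keep the per-protocol analysis (80% of training) as a sensitivity analysis.
- **Missing data.** State that the model assumes values are missing at random.
- **Scale.** Analyse cTnT and NT-proBNP on the log scale and report ratios.

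The cost is a minor SAP rewording; no new visits or data are needed. There are two downsides to accept openly. The result rests on the missing-at-random assumption, which unequal loss between arms could strain. The main analysis population for these outcomes also changes, which is a decision of substance and should be recorded as such.
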